5.2.6 Other subject characteristics

5.2.6.1 Chest X-Ray

Collected at screening and EOT visit in the Chest X-Ray eCRF. No definitions and derivations (other than treatment day of assessment) necessary. Any resulting findings are recorded as adverse event (or medical history).

5.2.6.2 Reproductive system findings

Data will be taken from the eCRF. No definitions and derivations (other than treatment day of assessment) necessary.

Includes all information mapped to RP SDTM domain (reproductive system findings) including Childbearing potential / Fertility from Demographics eCRF.

5.3 Study treatment exposure and compliance

Exposure and compliance information will be taken from the Study Drug Log eCRFs:

- **Up-titration Summary eCRF** (collects information on up-titrations conducted as planned as per protocol, recording start and end date of up-titration);
- **Up-titration Ponesimod/Placebo eCRF** (collects information on up-titration if not conducted as planned as per protocol, separately for up-titration tablets on daily basis);
- **Up-titration Teriflunomide/Placebo eCRF** (collects information on up-titration if not conducted as planned as per protocol, separately for up-titration capsules on daily basis);
- **Maintenance Ponesimod/Teriflunomide eCRF** (collects information on maintenance study drug intake based on maintenance capsules).

To derive the study treatment start date and time, in addition information collected on Study drug administration eCRFs ('Study Drug Administration - Randomization/Day 1', 'Study Drug Administration', 'Study Drug Administration - Re- Initiation' eCRF) is considered.

In addition, subjects filled an electronic study treatment diary (eDiary). Sites were instructed to review the entries in the subject study treatment diary versus the protocol-mandated drug intake regimen and versus the number of tablets and capsules dispensed and returned. Any discrepancy was to be clarified during the site visits, and actual drug intake was to be recorded in the eCRF, hence the information from the eCRF is considered to be the most reliable, and all exposure derivations including derivation of EOT date are only based on eCRF data.

5.3.1 Exposure

Study treatment start date is defined as the earliest study drug start date documented in the study drug administration or study drug log eCRF pages, as listed above.

The time of study treatment start (time of first exposure to treatment) is taken from the study drug administration eCRF, where the date is equal to the study treatment start date, if available.

The EOT date is defined as the latest study treatment end date, as recorded on the Study Drug Log (SDL) eCRFs listed above.

The following exposure variables are derived:

Duration of Study Treatment (days) = EOT date - Study treatment start date + 1 day. Duration of Study Treatment is also derived in weeks (days divided by 7), months (days divided by 30.4375), and years (days divided by 365.25).

Duration of Study Treatment is categorized as follows: ≤ 24 weeks (168 days), > 24 weeks to ≤ 60 weeks (420 days), > 60 weeks to ≤ 84 weeks (588 days), > 84 weeks to ≤ 108 weeks (756 days), > 108 weeks (756 days).

‘**Study treatment exposure, interruptions excluded**’ equals the ‘Number of days with intake documented’ for a subject overall as defined as part of the compliance derivations described in Section 5.3.2.1.

5.3.2 Compliance with study treatment

5.3.2.1 Compliance as percentage of days on study drug

Compliance is assessed as the percentage of days from the date of first intake until EOT with study drug intake documented in the eCRF:

$$\frac{\text{no. of days with intake documented}}{(\text{date of EOT-study treatment start date}) + 1 \text{ day}} \times 100$$

Note: Compliance below 100% must not be indicative of a deviation from the protocol since the protocol mandates dose interruptions for certain very specific safety scenarios as well as based on investigator’s judgment.

For reporting, the calculated compliance is categorized as follows: 100%, 90% – $< 100\%$, 80% – $< 90\%$, 50% – $< 80\%$, $> 0\%$ – $< 50\%$, 0%.

The number of days with study drug intake documented is derived as follows:

During up-titration period

The number of days with intake documented is based on entries on the eCRF ‘Up-titration Summary’ and/or ‘Up-titration Ponesimod/Placebo’ or ‘Up-titration Teriflunomide/ Placebo’, with separate entries for tablets (Ponesimod/Placebo) and capsules (Teriflunomide/ Placebo).

Only the intake of the dose form with active drug is considered.

For subjects where the investigator confirmed the up-titration has been conducted as planned, the ‘Up-titration Summary’ eCRF is filled, collecting only start and end date of the entire titration period without collecting ‘number of capsules taken’ or ‘number of tablets taken’. In that case the ‘Number of days with intake documented’ is derived and considered to be ‘titration end date – titration start date + 1 day’.

For all other subjects, information is collected on the ‘Up-titration Ponesimod/Placebo’ or ‘Up-titration Teriflunomide/Placebo’ eCRF, ‘Treatment start date’ resulting in potentially

multiple records of up-titration drug intake (collecting in addition ‘number of capsules taken’ or ‘number of tablets taken’). In that case ‘Number of days with intake documented’ for each record is derived in the same way as during the maintenance period but based on the dose form with active drug only.

During maintenance period

As per protocol, one capsule of study drug is to be taken per day. On the ‘Maintenance Ponesimod/Teriflunomide’ eCRF log form, each record collects ‘Treatment start date’, ‘Treatment end date’, and ‘Number of capsules taken’. If, for a record, the ‘Number of capsules taken’ is \leq ‘Treatment end date’ – ‘Treatment start date’ + 1, it is assumed that the ‘Number of capsules taken’ represents the ‘Number of days with intake documented’ during that record’s period of study drug intake. If, for a record, the ‘Number of capsules taken’ is $>$ ‘Treatment end date’ – ‘Treatment start date’ + 1, ‘Number of days with intake documented’ is set to ‘Treatment end date’ – ‘Treatment start date’ + 1 for the compliance calculation. These subjects are flagged as having taken $>$ 1 capsule per day on at least one occasion.

The ‘Number of days with intake documented’ for a subject overall is derived as the sum across all study drug log records (sum across up-titration, or maintenance records; multiple periods of study drug intake during up-titration or maintenance are possible, e.g., due to interruptions, or detailed up-titration eCRF filled).

5.3.2.2 Other compliance variables

Compliance to up-titration regimen based on eCRF

For each episode of up-titration, a subject is considered as **not having complied with the up-titration scheme** if either of the following is documented in the study drug log eCRFs for the kit containing active drug:

- Premature permanent study drug discontinuation (documented as reason for treatment end in at least one instance in the up-titration eCRF drug log);
- Capsule or Tablet (whatever corresponds to the active drug) is taken in an incorrect sequence during the up-titration (documented as reason for treatment end ‘Up-titration scheme not followed (other than interruption)’ in at least one instance in the up-titration eCRF drug log);
- 1 or more tablets or capsules are missed during the up-titration (‘temporarily interrupted’ documented as reason for treatment end at least one instance in the up-titration eCRF drug log);
- More than one tablet or capsule taken on any day during the up-titration;
- Up-titration lasted $<$ 13 days based on duration of up-titration period (see definition below);
- Up-titration lasted $>$ 15 days based on duration of up-titration period (see definition below).

Duration of up-titration is derived as last titration end date - first titration start date for each up-titration period.

Other compliance variables during maintenance period

The following deviations from the protocol-intended study drug maintenance are identified from the 'Maintenance Ponesimod/Teriflunomide' eCRF log form and flagged on a subject basis:

- More than 1 capsule of study drug taken per day on at least one occasion (derivation see above);
- At least one occasion of treatment interruption of more than 3 days documented, but maintenance treatment resumed or started without up-titration. This includes occasions when maintenance treatment started more than 4 days after the day up-titrations stopped.

5.3.3 Study treatment adjustments or interruptions

Study-specific criteria for interruption and discontinuation of study treatment were pre-specified in the protocol [section 5.1.13]. The protocol did not allow any study treatment dose adjustments.

Study treatment interruptions are assessed via the compliance variables described in Section 5.3.2 and the assessment adverse events leading to changes in study treatment as described in Section 5.5.5.

Subjects with at least one interruption: Derived as subjects with 'Study treatment exposure, interruptions excluded' < 'Duration of Study Treatment', based on the definitions in Section 5.3.1.

Total duration of interruption(s) (days) is derived as 'Duration of Study Treatment' - 'Study treatment exposure, interruptions excluded'.

Interruptions with reported reason are those where the reported reason for treatment end in the study drug log is 'Temporarily interrupted due to an AE', or 'Temporarily interrupted not due to an AE'.

5.4 Efficacy variables

5.4.1 Primary efficacy variable(s): ARR up to EOS

The primary endpoint is the Annualized Relapse Rate (ARR) up to EOS, based on confirmed relapses according to the treating neurologist / principal investigator. ARR is defined as the number of confirmed relapses per subject-year.

For subjects completing the study as planned the EOS is scheduled to occur at least 108 weeks (± 7 days) after randomization.

More precisely, for subjects prematurely discontinuing treatment the EOS is scheduled to occur 108 weeks (± 7 days) after randomization. For subjects completing the 108-week treatment period the EOS is scheduled to occur prior to entry into the open-label extension (14–22 days after EOT, or 23–37 days after EOT in exceptional cases) or after the safety follow-up period for subjects not entering the open-label extension (30–37 days after EOT).

A confirmed relapse is defined as a record with ‘Relapse meeting the criteria for a confirmed relapse?’ answered ‘Yes’ on the ‘Relapse Summary’ eCRF. All confirmed relapses from randomization up to EOS will be included in the analysis.

For the statistical analysis of ARR, the following data will be used:

- Number of confirmed relapses from date of randomization up to EOS date;
- Length of observation expressed in years, defined as: $[\text{EOS date} - \text{date of randomization} + 1]$ in days, divided by 365.25.

The logarithm of the length of observation up to EOS will be used as an offset variable in the primary efficacy and sensitivity analyses.

Confirmed relapses ‘from date of randomization up to EOS date’ includes all confirmed relapses unless starting prior to randomization.

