9.6.3 Main analysis

The primary statistical analysis will be performed up to EOS on the FAS using an NB regression model for confirmed relapses, with treatment as a factor and the binary stratification variables (EDSS \leq 3.5 versus EDSS $>$ 3.5; DMT within last 2 years prior to randomization [Yes/No]) and the number of relapses in the year prior to study entry (categories \leq 1 [or missing, in order to avoid excluding subjects from the analysis] and \geq 2) included in the model. The model also includes an offset variable defined as the log of time on study (in years) from randomization up to EOS. The primary null hypothesis will be tested with a two-sided alpha level of 1% for conclusive evidence and 5% for a positive study.

Mean model-based estimates of the ARR (for confirmed relapses), by treatment arm, as well as 99% CIs and 95% CIs are presented. A rate ratio comparing ponesimod 20 mg with teriflunomide 14 mg will be derived from the model including 99% CIs, 95% CIs and the corresponding p-value. The dispersion parameter will also be displayed.

Descriptive summary statistics of the number of confirmed relapses as a continuous variable and the number of confirmed relapses in categories (0, 1, 2, 3, 4, ≥ 5), by treatment arm will be presented. The total cumulative number of confirmed relapses, as well as the total cumulative time on study (summed for all subjects) will also be displayed. From the total number of confirmed relapses and the total time on study the raw unadjusted ARR, by treatment arm, will be calculated and summarized.

The fit of the model will be assessed and other distributions such as the Poisson distribution will be considered in case of a lack of fit. The treatment-by-covariate interactions will also be assessed in separate models; if the interaction p-value is < 0.01 it will be investigated further to determine the nature of the interaction (quantitative or qualitative).

Handling of study discontinuation

For the main analysis it is assumed that follow-up time after study discontinuation is missing at random: a hypothetical scenario is considered assuming that subjects who discontinued the study would have similar efficacy as the subjects from the same treatment group who did not discontinue the study.

Sensitivity analyses on this assumption are described in Section [9.6.4](#).

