9.6.4.2 ARR based on confirmed relapses up to EOS including derived stratification variable

Same analysis as for the main analysis, but instead of adjusting for the stratification variables from the IRT adjust for eCRF-derived stratification variables.

This analysis was requested by the FDA for the SPA review of study AC-058B302 and is performed to ensure that the results are consistent with the primary analysis, which are adjusted for the IRT stratification variables and – after eCRF data cleaning – might not match.

9.6.4.3 *ARR imputation analysis for subjects withdrawing from the study prematurely (imputation from EOS to theoretical Week 108)*

To assess the impact of subjects withdrawing from the study prior to Week 108, sensitivity analyses will be performed. These include the imputation of confirmed relapses using various assumptions for the period with missing data.

The proportion of missing data, i.e., missing observation time, will be calculated as

$$1 - \frac{\text{Cumulative time between randomization and EOS (or theoretical Week 108, if earlier)}}{\text{Cumulative time between randomization and theoretical Week 108}}$$

and will be summarized descriptively. Time up to EOS (i.e., time in study) will be presented based on an inverse cumulative distribution function [see Section 9.3.1].

Multiple imputation (MI) methods for count data are applied, following the approach from Keene 2014; see Section 10.1.1 for details.

Number of relapses between EOS and theoretical Week 108 will be imputed for subjects who have prematurely discontinued from the study.

Several approaches will be used for the imputation of events:

- **Missing at random (MAR) MI approach:** Under this approach, the rate after withdrawal for each treatment arm is assumed to be the rate in the respective arm before withdrawal.
- **Reference-based MI approaches:** The rate in the reference (teriflunomide 14 mg) arm is used for imputation in both the ponesimod 20 mg and teriflunomide 14 mg arms. While the post-withdrawal events in the teriflunomide 14 mg arm are imputed under the MAR assumption for that arm, two different approaches are applied for the imputation of the post-withdrawal events in the ponesimod arm:

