 - a. **Copy reference MI approach:** Impute based on the reference arm; For a subject in the ponesimod arm, if the event rate prior to withdrawal is *better than would be expected on the reference arm*, under this approach, their imputed event rate after withdrawal will also be *better than the expected event rate on the reference arm*. The copy reference imputation is expected to be less favorable for ponesimod 20 mg as compared to MAR approach as it is relative to the rate in the reference arm, but not as extreme as the jump to reference approach described below.
 - b. **Jump to reference MI approach:** Impute based on the reference arm; For a subject in the ponesimod arm, if the event rate prior to withdrawal is *worse than would be expected on the ponesimod arm*, under this approach, their imputed event rate after withdrawal will be *worse than the expected event rate on the reference arm*. This approach assumes that withdrawn subjects on the ponesimod

20 mg treatment will quickly lose any positive effect of their treatment (relative to the reference arm) when it is stopped.

The resulting rate ratio and corresponding 99% and 95% CIs will be reported and presented in tables and graphically.

A delta-adjustment MI method [Keene 2014] will also be applied to further assess deviations from the MAR assumption:

- **Delta adjustment MI approach:** Starting with the MAR assumption for both treatment arms, a 2-way delta adjustment is applied.

Ponesimod 20 mg arm: The rate after withdrawal is multiplied by δ_P , ranging from 1 (MAR, i.e. same rate as prior to withdrawal) to 3.1 (~Tripling of relapse rate) in steps of 0.3.

Teriflunomide 14 mg arm: The rate after withdrawal is multiplied by δ_T , ranging from 0.1 (relapse rate reduced by 90%) over 1 (MAR, i.e. same rate as prior to withdrawal) to 3.1 (~tripling of relapse rate) in steps of 0.3.

For each imputed dataset the same negative binomial regression model as for the primary analysis will be fit and results will be combined using Rubin's rule [see Section 10.1.1].

The resulting rate ratios and corresponding 99% CIs and p-values will be reported and presented in tables and graphically.

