9.7.2.3 Supportive/sensitivity analyses

9.7.2.3.1 Analysis of CUALs from baseline to EOS - Missing data sensitivity: Imputation from last MRI scan to Week 108

To assess the impact of missing data on CUAL, i.e., last MRI scan conducted prior to Week 108, sensitivity analyses will be performed. These include the imputation of CUALs between last MRI scan and the theoretical Week 108 using different assumptions for the period with missing data on the FAS.

Time up to the last MRI scan is presented with a cumulative distribution function by treatment arm.

Sensitivity analyses for the main analysis will be conducted based on the MI method for negative binomial count data [see Section 10.1.1].

For subjects with missing Week 108 MRI scan the number of CUALs from last MRI scan up to the theoretical Week 108 will be imputed under different assumptions.

For all MI methods, subjects without a post-baseline MRI scan will be imputed based on baseline covariates; they will not be excluded from the analyses. No imputation is performed for subjects with missing baseline MRI; they are excluded from the analyses.

Imputation of events is conducted under the following assumptions: Missing at Random (MAR), Copy reference, Jump to reference. The corresponding interpretations are detailed in Section 9.6.4.3, only that imputation is now conducted post last MRI scan instead of post study-withdrawal.

For each imputed dataset the analysis is adjusted for the same covariates as for the main analysis, i.e., the binary stratification variables (EDSS \leq 3.5 versus EDSS $>$ 3.5; DMT within last 2 years prior to randomization [Yes/No]) and Gd+ T1 lesions at baseline (absent or present).

The rate ratio estimates with corresponding 95% CIs will be computed for each method.

9.7.2.3.2 *Analysis of CUAL - per protocol analysis*

The main analysis will be repeated using a per protocol analysis approach, i.e., on the PPS and considering MRI scans up to the first deviation leading to exclusion from the per protocol analysis. The number of CUALs (per protocol) is used as a response variable and the log of the time to the last MRI scan (years) considered in the per-protocol analysis as an offset variable [see Section 5.4.2.2]. Covariate adjustment as for the main analysis will be applied.

9.7.2.3.3 *Analysis of CUALs from baseline to EOT + 7 days*

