10.1.1 Imputation methods for count data

Multiple imputation for count data will be applied for sensitivity analyses of the primary and secondary count data.

A multiple imputation approach following [Keene 2014](#) is followed, count data being assumed to follow a negative binomial distribution. Implementation will be based on a SAS Macro publicly available [see [Roger 2017](#)].

The general multiple imputation is a 3-step approach:

(i) Create n_{impute} imputed datasets. Details are specified below in the imputation algorithm.

(ii) Analyze each imputed dataset using a negative binomial model as for the corresponding main analysis. (Details such as response, covariates, and offset are specified per analysis).

(iii) Derive multiple imputation inferential statistics by combining step (ii) results using Rubin's rules.

In step (iii) the rate ratio with corresponding CI (99% and/or 95%) will be derived.

For creation of the imputed datasets in step (i) the following imputation algorithm will be followed:

Imputation algorithm for negative binomial count data

1. Fit a bayesian log-linear negative binomial regression model on non-missing data,
 - For imputation between EOS and Week 108 fit to count data up to EOS; for imputation between EOT+7 and Week 108 fit to count data up to EOT + 7;
 - Use logarithm of time (in years) as an offset variable, treatment as a factor and adjust for covariates as for the main analysis;
 - Use non-informative priors for the model parameters (Default option for proc genmod with bayes statement);
 - Generate samples for the model parameters (linear regression parameters β and dispersion parameter k) from the posterior distribution using MCMC (seed = 24092010).

The following initial MCMC specifications will be used: 1000 burn-in iterations ($n_{bi} = 1000$), 20000 iterations after burn-in ($n_{mc} = 20000$), with a thinning of 5 ($thin = 5$). This yields a total of 4000 posterior draws ($n_{mc} \div thin$), which corresponds to the number of multiple imputations ($n_{impute} = 4000$). The MCMC specifications, may be adjusted based on diagnostic checks for the Bayesian model.

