2. Impute the count data for the missing follow-up time conditional on the follow-up information available based on the parameter estimates samples from step 1, under the considered assumption (MAR, copy reference, jump to reference, or delta adjustment). The conditional distribution follows also a negative binomial distribution; see [Keene 2014](#) for details (seed = 30112013).
3. Derive the overall imputed count variable by adding up the observed count data (e.g., confirmed relapses up to EOS for imputation between EOS and Week 108) and the simulated count data for the missing follow-up time (from step 2).
4. Repeat this n_{impute} times to obtain n_{impute} complete datasets.

Imputation based on baseline covariates only

Imputation based on baseline covariates only (required for imputation of CUALs from baseline to Week 108 for subjects without any post-baseline MRI scan) can be implemented with the above algorithm as follows: Subjects with missing information are included in the input dataset with count variable of zero and time variable of zero. Interpretation is that no events (e.g., CUALs) have been observed since baseline for zero follow-up time. The imputation algorithm steps 2–3 will impute the counts for the entire time period from randomization to Week 108 which is the missing follow-up time in this case. The conditional distribution simplifies in this case to the marginal distribution and thus imputation will be based on baseline covariates only [see [Keene 2014](#)]. Note that in step 1 of the imputation algorithm, these zero follow-up time records will be ignored when fitting the Bayesian negative binomial regression model as the offset (log of the follow-up time) does not exist.

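### The offset written for the sensitivity analyses (log time to EOS) does not match imputed relapse counts that run to Week 108, and no section names the offset for the completed datasets

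*SAP*

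**What the plan says.** - **Section 5.4.1** defines the primary variable as confirmed relapses and observation time from randomization to EOS, then adds: "The logarithm of the length of observation up to EOS will be used as an offset variable in the primary efficacy and sensitivity analyses".
- **Section 9.6.3**, primary negative binomial (NB) model: "The model also includes an offset variable defined as the log of time on study (in years) from randomization up to EOS".
- **Section 9.6.4.3**, under the heading for sensitivity analyses: "Number of relapses between EOS and theoretical Week 108 will be imputed for subjects who have prematurely discontinued from the study". The model for the completed data is fixed by reference: "For each imputed dataset the same negative binomial regression model as for the primary analysis will be fit".
- **Section 10.1.1**, imputation algorithm: the imputation model itself uses observed data only ("For imputation between EOS and Week 108 fit to count data up to EOS"). Step 3 then builds the response: "Derive the overall imputed count variable by adding up the observed count data", to which the simulated count for the missing time is added. For the analysis of each completed dataset (step ii) it says: "Details such as response, covariates, and offset are specified per analysis".
- **Section 9.6.5.1** imputes from EOT + 7 days to theoretical Week 108. The only offset it gives is log time to EOT + 7 days.
- **Section 9.7.2.3.1** imputes CUALs from the last MRI to theoretical Week 108, carries over the covariates of the main analysis and names no offset. It adds that "subjects without a post-baseline MRI scan will be imputed based on baseline covariates; they will not be excluded from the analyses". The offset of the main CUAL analysis (9.7.2.2) is log time to last MRI.

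**The concern.** An NB rate model needs the count and the offset to refer to the same period. In the imputed ARR datasets a withdrawn subject's count runs to Week 108, while the only offset written down for that analysis stops at EOS. The subject's rate is then too high, and the more so the earlier the withdrawal.

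The MAR, copy-reference, jump-to-reference and delta analyses of 9.6.4.3 are where the plan tests the missing-data assumption stated in 9.6.3. A MAR imputation should reproduce the primary result, and the reference-based versions should move it toward the null. With a mismatched offset the rate ratio also picks up the difference in withdrawal between arms. If teriflunomide subjects withdraw more, a jump-to-reference analysis can look better for ponesimod than the primary analysis. If ponesimod subjects withdraw more, robustness can be understated.

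**Working it through.** **1. Which offset do the words give?** Section 9.6.4.3 is a sensitivity analysis, so the 5.4.1 sentence reaches it. It fits the primary model, and 9.6.3 gives that model's offset as time to EOS. Section 10.1.1 defers the offset to the analysis sections. Where the ARR observation period changes elsewhere, the SAP names the new offset: EOT + 7 days (9.6.5.1), per protocol (9.6.5.2), start of a new DMT (9.6.5.4), post-treatment (9.6.5.6) and time periods (9.6.5.7). Section 9.6.4.3 names none, and 5.4.1.2 defines no time-to-Week-108 variable. An EOS offset is correct in step 1 of the imputation, which uses observed counts. The gap is in step (ii).

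**2. One subject.** Week 108 is Day 756 (5.7.2), or 756/365.25 = 2.07 years. For withdrawal at day 378 the completed count covers 756 days and the EOS offset covers 378. The rate is multiplied by 756/378 = 2.0.

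**3. Hand check of an arm.** Assume withdrawal uniform over days 1–756 (mean about day 378) and completers followed to day 786 (Week 108 plus 30 days). The crude inflation is the mean time covered divided by the mean time to EOS.
- 15% withdrawal: (0.85×786 + 0.15×756)/(0.85×786 + 0.15×378) = 781.5/724.8 = 1.078.
- 20%: 780.0/704.4 = 1.107. 10%: 783.0/745.2 = 1.051.
- 20% ponesimod against 10% teriflunomide: rate ratio multiplied by 1.107/1.051 = 1.05.

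The NB fit gives short-follow-up subjects relatively more weight than this crude ratio does, so somewhat larger shifts are expected.

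**4. Simulation.** The same imputed counts were fitted twice, once with a Week 108 offset and once with the literal EOS offset. The SAP gives no withdrawal rates, so all inputs are assumed.
- Set A: 1133 subjects, ARR 0.21 vs 0.30, dispersion 1.
- Set B: 40,000 per arm, ARR 0.20 vs 0.30, dispersion 1, imputation at the true parameters, treatment the only covariate.

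| Withdrawal, ponesimod / teriflunomide | MAR rate ratio, Week 108 → EOS offset | Jump to reference, Week 108 → EOS offset |
|---|---|---|
| A: 12% / 12% | 0.704 → 0.701 | – |
| B: 15% / 15% | 0.651 → 0.645 | 0.682 → 0.684 |
| A: 18% / 10% | 0.696 → 0.730 (+5%) | 0.720 → 0.763 (+6%) |
| B: 20% / 10% | 0.669 → 0.712 (+6%) | 0.705 → 0.762 (+8%) |
| A: 10% / 18% | 0.688 → 0.642 (−7%) | 0.702 → 0.660 (−6%) |
| B: 10% / 20% | 0.658 → 0.606 (−8%) | 0.670 → 0.620 (−7%) |

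Arm-level ARRs under MAR with balanced withdrawal:
- A: 0.301 → 0.327 and 0.212 → 0.230 (about +9% each).
- B: 0.303 → 0.337 and 0.197 → 0.218 (about +11% each). Estimated dispersion rises from 1.02 to 1.16.

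With the Week 108 offset in set B, MAR reproduces the observed-data rate ratio: 0.651 vs 0.653, 0.669 vs 0.672 and 0.658 vs 0.658 for the three withdrawal patterns.

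**5. CUAL.** Subjects with no post-baseline MRI have zero observed time. Section 10.1.1 itself notes that the log offset does not exist for them, but deals with this only in step 1. If the main analysis's last-MRI offset were used in step (ii), they would drop out, against 9.7.2.3.1.

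**The case against.** Much in the SAP points to the right offset. Section 10.1 defines the count as the events occurring within the subject's own length of observation, with the log of that length as offset. Section 9.6.4.3 measures missing time against theoretical Week 108 and describes MAR as an unchanged rate after withdrawal, which an EOS offset would contradict. The CUAL rule that subjects without a scan stay in is workable only with the longer period. The 5.4.1 sentence can also be read as covering only analyses of the observed count, since the EOT + 7 analyses have their own offset. All of this stands. The plan is internally inconsistent and incomplete on this point; it is not a deliberate instruction to use EOS time.

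A reader might therefore infer more than the documents support:

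- **That the sensitivity results will come out wrong.** This follows only if the 5.4.1 and 9.6.4.3 wording is applied literally. Section 10.1.1 bases implementation on a published method and a public SAS macro, whose handling of the offset cannot be seen here.
- **That the reported treatment effect is always distorted.** Section 9.6.4.3 reports the rate ratio, which barely moves when withdrawal is balanced.
- **That the EOT + 7 imputation is distorted at least as much.** This was not calculated. The shift in the rate ratio depends on imbalance between arms, not on total missing time alone.
- **That the primary result or the alpha strategy is at risk.** Neither uses imputed counts.

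These limits do not remove the conflict. The explicit sentence in 5.4.1 gives a mismatched offset, and no analysis section overrides it.

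**Conclusion.** The point holds as a conflict in the text that needs a wording correction. Read literally, 5.4.1 and 9.6.4.3 pair a count to Week 108 with time to EOS for withdrawn subjects, against the general model in 10.1. Under assumed inputs (ARR about 0.2 vs 0.3, dispersion 1, uniform withdrawal), arm ARRs are inflated by about 8–11% at 12–15% withdrawal. The MAR and reference-based rate ratios are almost unchanged if withdrawal is balanced, and shift about 5–8% in either direction if it differs by 8–10 percentage points. The same gap exists in the EOT + 7 and CUAL imputations, where its size was not computed. The primary analysis is not affected.

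**What to change.** - In 5.4.1, limit the sentence on the EOS offset to analyses of observed data.
- In 9.6.4.3, 9.6.5.1, 9.7.2.3.1 and step (ii) of 10.1.1, state that in completed datasets the offset is the log of the period each subject's count covers:
  - subjects with imputed time, including CUAL subjects with no post-baseline MRI: randomization to theoretical Week 108;
  - all others: the observed time of the corresponding main analysis (to EOS, EOT + 7 days or last MRI).
- Do not use a blanket maximum of observed time and Week 108. A completer whose final visit or scan fell early in its window has nothing imputed, and the maximum would add time without counts, a small error in the opposite direction.

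Cost: a few sentences and one derived time variable per imputed analysis. No new data are needed, and the primary analysis does not change.
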